Abbreviations: AIM = Acceptability of Intervention Measure; ASA=Alternative Site of Administration; FIM = Feasibility of Intervention Measure; IC = infusion center; QAP = Qualitative Analysis Plan

2 Study Design

This is a Phase 4, single-arm, open-label, multi-center study examining the administration of CABENUVA IM in ICs/ASAs in the United States. This study is being conducted following Food and Drug Administration (FDA) approval and commercial availability of CABENUVA. Eligible and consenting PLWHIV will be followed for eight months to evaluate an implementation blueprint for IM administration of CABENUVA for HIV-1 treatment at ICs/ASAs. The total duration for study PLWHIV is approximately eight months from the time of enrollment and receipt of the first administration of CABENUVA IM injections at the IC/ASA.

Relevant to this SAP, up to 120 PLWHIV who have been prescribed CABENUVA by their HIV care provider will be asked to complete questionnaires per the Schedule of Activities (SoA; see ANNEX 1 in protocol), as follows:

- Baseline/Month 1 questionnaires should be completed prior to receiving the first CABENUVA injections
- Baseline/Month 1 for each PLWHIV is defined as the date when a PLWHIV signs the informed consent form and completes Baseline/Month 1 protocol procedures prior to receiving the first CABENUVA injections at the IC/ASA
- Months 3 and 8 will be anchored off of each PLWHIV Baseline/Month 1 visit, so it will reflect the Months on study, regardless of what dose they are on and regardless of whether they have missed any injections and received oral bridging.

PLWHIV questionnaires consist of the Feasibility of Intervention Measure (FIM) and the Acceptability of Intervention Measure (AIM), as well as a tailored questionnaire.

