2.4 Implementation Science-Related Protocol Deviations

Implementation science-related protocol deviations will be reported, where numerators equal the number of PLWHIV experiencing the respective deviation type, and denominators equal the number of PLWHIV in analytic dataset. Deviations reported will include, but are not limited to, the following:

questionnaires with missing data, questionnaires completed but not required at respective time point, questionnaires completed out of window (early), questionnaire completed out of window (late), and duplicate questionnaire completed. Missing data is considered a deviation if any item is missing, and the participant has not dropped out of the study. See section 2.3 and 3.1 for how deviations affect inclusion in analytic dataset.

3 Statistical Methods

This SAP has been developed to guide the analyses for the data collected and assumes that all data will be collected in adherence to the protocol developed by GSK/ViiV. The analysis population is all PLWHIV who complete any portion of any questionnaire at any point in the study. As the data are analyzed, some deviation from expectations may occur. In instances where these deviations would make the proposed analyzes inappropriate, modifications to the SAP—along with justifications for these changes—will be made and noted in the final report.

Continuous and interval-like variables will be summarized using descriptive statistics (e.g., n, mean, standard deviation [SD], median, minimum, maximum, first and third quartiles, and confidence intervals [CIs]). Data in tables will be tabulated relative to the source data. Mean, median, and quartiles will be tabulated to one more decimal place than the source data; minimum/maximum values will have the same decimal places as source data; percentages will be rounded to one decimal place after calculation. SD and CIs will be tabulated to two more decimal places than the source data. Categorical variables will be reported as frequency counts, the percentage of PLWHIV in corresponding categories, and 95% CIs.

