NOTE: Missing for individual item counts = the number of participants who were eligible to complete a survey at the respective timepoint but did not complete respective item; Missing % = the number of participants who were eligible to complete a survey at the respective timepoint but did NOT complete the respective item / the number of people who filled out any portion of a survey the respective timepoint. Missing for the mean score counts any instance where a respondent completed one FIM item, not reaching the minimum of 2 items required to calculate a mean FIM score.

Table 3.2. PLWHIV, Distributional Characteristics of Acceptability of Intervention Measure (AIM), N=XX

Item/ Scale	Time Point	Number of Participants	Missing	Mean	SD	Median (Q1, Q3)	Range (–Min, Max)	Percent Missing	Percent Floor	Percent Ceiling	95% Cl (Lower, Upper)
	BL	XX	XX	XX	XX	XX (X.X, X.X)	(X.X, X.X)	XX%	XX%	XX%	(X.X,X.X)
AIM Mean Score	M3	XX	XX	XX	XX	XX (X.X, X.X)	(X.X, X.X)	XX%	XX%	XX%	(X.X, X.X)
	M8	XX	XX	XX	XX	XX (X.X, X.X)	(X.X, X.X)	XX%	XX%	XX%	(X.X, X.X)
1. The idea of providing	BL	XX	XX	XX	XX	XX (X.X, X.X)	(X.X, X.X)	XX%	XX%	XX%	(X.X, X.X)
CABENUVA at my infusion center meets my	M3	XX	XX	XX	XX	XX (X.X, X.X)	(X.X, X.X)	XX%	XX%	XX%	(X.X, X.X)
approval.	M8	XX	XX	XX	XX	XX (X.X, X.X)	(X.X, X.X)	XX%	XX%	XX%	(X.X, X.X)
2. The idea of providing	BL	XX	XX	XX	XX	XX (X.X, X.X)	(X.X, X.X)	XX%	XX%	XX%	(X.X, X.X)
CABENUVA at my infusion	M3	XX	XX	XX	XX	XX (X.X, X.X)	(X.X, X.X)	XX%	XX%	XX%	(X.X, X.X)
center is appealing to me.	M8	XX	XX	XX	XX	XX (X.X, X.X)	(X.X, X.X)	XX%	XX%	XX%	(X.X, X.X)
3. I like the idea of	BL	XX	XX	XX	XX	XX (X.X, X.X)	(X.X, X.X)	XX%	XX%	XX%	(X.X, X.X)
providing CABENUVA for PLWHIV in my infusion	M3	XX	XX	XX	XX	XX (X.X, X.X)	(X.X, X.X)	XX%	XX%	XX%	(X.X, X.X)
center.	M8	XX	XX	XX	XX	XX (X.X, X.X)	(X.X, X.X)	XX%	XX%	XX%	(X.X, X.X)
4. I welcome providing	BL	XX	XX	XX	XX	XX (X.X, X.X)	(X.X, X.X)	XX%	XX%	XX%	(X.X, X.X)
CABENUVA for PLWHIV in	M3	XX	XX	XX	XX	XX (X.X, X.X)	(X.X, X.X)	XX%	XX%	XX%	(X.X, X.X)
my infusion center.	M8	XX	XX	XX	XX	XX (X.X, X.X)	(X.X, X.X)	XX%	XX%	XX%	(X.X, X.X)

Abbreviations: AIM = Acceptability of Intervention Measure; BL = Baseline; CI = confidence interval; M3 = Month 3; M8 = Month 8; PLWHIV = Participants living with human immunodeficiency virus; SD = standard deviation.

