Percent Floor for the mean score is the percent of respondents with a score of 1 out of all respondents replying to at least two AIM items at a given time point. Percent Ceiling for the mean score is the percent of respondents with a score of 5 out of all respondents replying to at least two AIM items at a given time point. NOTE: Missing for individual item counts = the number of participants who were eligible to complete a survey at the respective timepoint but did not complete respective item; Missing % = the number of participants who were eligible to complete a survey at the respective timepoint but did NOT complete the respective item / the number of people who filled out any portion of a survey the respective timepoint. Missing for the mean score counts any instance where a respondent completed one AIM item, not reaching the minimum of 2 items required to calculate a mean AIM score.

Table 4.1. PLWHIV, Univariate Distribution of Feasibility of Intervention Measure (FIM), N=XX

Items	Time Point	Number of Participants	Missing	Completely disagree	Disagree	Neither agree nor disagree	Agree	Completely agree
1. Administering CABENUVA	BL	XX	n (%)	n (%)	n (%)	n (%)	n (%)	n (%)
seems implementable in my	M3	XX	n (%)	n (%)	n (%)	n (%)	n (%)	n (%)
infusion center.	M8	XX	n (%)	n (%)	n (%)	n (%)	n (%)	n (%)
2. Administering CABENUVA	BL	XX	n (%)	n (%)	n (%)	n (%)	n (%)	n (%)
seems possible in my infusion	M3	XX	n (%)	n (%)	n (%)	n (%)	n (%)	n (%)
center.	M8	XX	n (%)	n (%)	n (%)	n (%)	n (%)	n (%)
3. Administering CABENUVA	BL	XX	n (%)	n (%)	n (%)	n (%)	n (%)	n (%)
seems doable in my infusion	M3	XX	n (%)	n (%)	n (%)	n (%)	n (%)	n (%)
center.	M8	XX	n (%)	n (%)	n (%)	n (%)	n (%)	n (%)
4. Administering CABENUVA	BL	XX	n (%)	n (%)	n (%)	n (%)	n (%)	n (%)
seems easy to implement in	M3	XX	n (%)	n (%)	n (%)	n (%)	n (%)	n (%)
my infusion center.	M8	XX	n (%)	n (%)	n (%)	n (%)	n (%)	n (%)

Abbreviations: BL = Baseline; M3 = Month 3; M8 = Month 8; PLWHIV = participants living with human immunodeficiency virus.

NOTE: Missing = the number of participants who are eligible to complete a survey at the respective timepoint but did not complete respective item; Missing % = the number of participants who were eligible to complete a survey the respective timepoint but did NOT complete the respective item / the number of people who were eligible to fill out a survey at the respective timepoint.

Table 4.2. PLWHIV, Univariate Distribution of Acceptability of Intervention Measure (AIM), N=XX

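### The item-level Missing % in participant SAP Tables 3.1 and 3.2 counts non-responders in the numerator but not the denominator, so it overstates missingness and will disagree with Tables 4.1 and 4.2 when eligible participants return no form

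*SAP*

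**What the plan says.** The participant SAP (Participants Living with HIV for Implementation Science Questionnaires) reports FIM and AIM item missingness in several table shells in its Section 6.

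- **Tables 3.1 and 3.2, notes.** For individual items, the numerator of Missing % is "the number of participants who were eligible to complete a survey at the respective timepoint but did NOT complete the respective item". The denominator is "the number of people who filled out any portion of a survey the respective timepoint". The mean-score row has its own count of missing: respondents who answered only one of the four items.
- **Tables 4.1 and 4.2, notes.** For the same items and timepoints, the numerator is the same in substance, but the denominator is "the number of people who were eligible to fill out a survey at the respective timepoint".
- **Staff SAP, Tables 3.1 and 3.2, notes.** These are the direct counterparts for infusion-center staff, and they use the eligible denominator.
- **HIV care provider SAP, Tables 3.1 and 3.2, notes.** These count only people who filled out some part of a survey at any time, in both numerator and denominator.

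Section 3 of the participant SAP sets the population: "The analysis population is all PLWHIV who complete any portion of any questionnaire at any point in the study". Its Section 2 gives the ceiling on numbers: "up to 120 PLWHIV who have been prescribed CABENUVA by their HIV care provider".

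**The concern.** A percentage missing should count cases from the same group that forms its base. The notes to Tables 3.1 and 3.2 take the numerator from everyone eligible and the denominator from those who returned something. The two bases agree only if everyone eligible returns a form.

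Complete return cannot be assumed. Membership of the analysis population needs only some part of one questionnaire at one timepoint, so a person can be in it and return nothing at Month 3 or Month 8. The clinical SAP (Section 2.1) also expects treatment discontinuations and missed injections over time.

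What is at stake is the description of non-response. The primary proportion is computed among participants who completed all four FIM items, with no imputation, so readers will look at item missingness to judge how far the Month 8 result can be trusted. Two tables giving different percentages for the same item, one of them too high, would make that harder.

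**Working it through.** There is no plan figure to reproduce, because the shells hold placeholders only. The check is on the formula.

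**Inputs**
- E = number eligible at the timepoint. Set to 120, the ceiling in Section 2 of the participant SAP.
- R = number who filled out any part of the survey at that timepoint (R ≤ E). Assumed; the documents give no value.
- s = responders who skipped the item. Assumed.

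**Formulas**
- Eligible participants without the item: (E − R) + s.
- Tables 3.1 and 3.2 as written: [(E − R) + s] / R.
- Tables 4.1 and 4.2: [(E − R) + s] / E.
- The first divided by the second is E / R. The written value is thus too high by the factor E/R, and the two agree only when R = E or nothing is missing.
- The s skippers are in both parts of the written ratio. The E − R people who returned nothing are in the numerator only.
- The written value exceeds 100% when (E − R) + s > R. With s = 0 this means R < E/2.

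**Results for E = 120**

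| R (assumed) | s (assumed) | Without the item | As written, over R | Over E |
|---|---|---|---|---|
| 120 | 6 | 6 | 6/120 = 5.0% | 5.0% |
| 108 | 0 | 12 | 12/108 = 11.1% | 10.0% |
| 96 | 4 | 28 | 28/96 = 29.2% | 23.3% |
| 90 | 0 | 30 | 30/90 = 33.3% | 25.0% |
| 80 | 0 | 40 | 40/80 = 50.0% | 33.3% |
| 60 | 0 | 60 | 60/60 = 100.0% | 50.0% |
| 59 | 0 | 61 | 61/59 = 103.4% | 50.8% |

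The first row shows that skipped items alone do no harm: with full return the two definitions coincide. The distortion comes entirely from people who return no form.

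**Mean-score row.** Its missing count covers only respondents with one item answered. All of them filled out part of a survey, so all are in the denominator and the mixed-base problem does not arise.

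**The case against.** Four points can be made on the other side.

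1. **Eligible is not defined.** If it meant those who returned a form, the two bases would match. Nothing in the participant SAP says so, and the note uses two different descriptions within one formula. A narrower version is more plausible: withdrawn participants may not count as eligible. Protocol Section 9.1 removes from the study anyone who permanently stops CABENUVA, and Section 2.4 of the participant SAP treats missing data as a deviation only for those who have not dropped out. That would lower E and shrink the distortion, but it would not remove it for those who stay in the study and return nothing.

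2. **Values above 100% are remote.** A reader might infer that the table will print impossible percentages. With no skipped items that needs more than half of those eligible to return nothing, and no document suggests such a level. Moderate inflation is the likelier result.

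3. **The primary result is untouched.** A reader might also infer that the Month 8 FIM proportion is at risk. It is not. Table 2.1 gives that proportion its own denominator, the number completing all four items, and the Missing % note enters neither the estimate nor its interval. Nor is Table 3.1 the only report of missingness: it also has a count column, Table 4.1 gives the percentage on the eligible base, and Appendix A Table A1 reports completed and missing by item, although its base is not stated.

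4. **Another consistent definition exists.** Responders could be used in both parts, s/R, as the provider SAP does in its own way. With R = 96 and s = 4 that gives 4/96 = 4.2%, which describes item skipping alone. The documents do not show which base the authors had in mind.

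The first three points limit the size and reach of the problem. The fourth bears on the choice of remedy. None of them makes the formula as written consistent.

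**Conclusion.** The definition is wrong as written, for the individual-item rows of participant Tables 3.1 and 3.2. Whenever at least one eligible participant returns no form, the printed Missing % is too high by the factor E/R and conflicts with Tables 4.1 and 4.2. With 120 eligible, 90 responders and no skips, all illustrative assumptions apart from the ceiling of 120, the excess is 8.3 percentage points (33.3% against 25.0%). With full return there is no error.

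This is a small inconsistency in a descriptive table. It affects how missingness is displayed, and no inferential result depends on it.

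**What to change.** In the notes to participant Tables 3.1 and 3.2, replace the denominator of the item-level Missing % with the number eligible to fill out a survey at the timepoint. This matches participant Tables 4.1 and 4.2 and staff Tables 3.1 and 3.2. Leave the mean-score row with its separate definition, and say in the note that the new denominator applies to item rows. It would help to add one sentence stating whether withdrawn participants count as eligible, since every eligible-based percentage depends on it.

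The cost is two footnote edits, plus that sentence if added. No new data or analysis is needed.

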3.1 Missing Data Handling Scheme

Missing data at the multi-item scale level for standardized scales (FIM and AIM) will be addressed with standard proration rules²: if at least 50% of the items are completed the scale will be scored by taking the mean of the completed items, unless otherwise specified for a particular outcome. Following this, partially completed FIM and AIM administrations will be scored if two, three, or four items are completed, and will not be scored if only one item is completed. Items not completed will be logged as

missing data. No missing data will be imputed. Table shells for missing data from FIM and AIM scales can be found in Appendix A.

3.2 Cross-sectional Univariate Distributions of Study Variables and Features of Score Distributions

For questions with ordinal responses, a univariate distribution of every item will be tabulated. Standard distributional statistics will be tabulated for interval-like (ordinal) variables, including mean, SD, median, percentage missing, range (minimum and maximum of responses), percentage of the sample at the ceiling (highest possible score) and floor (lowest possible score), first and third quartiles, and 95% CIs. For questions with descriptive responses, a frequency distribution of all responses will be presented with n (%).

3.3 Distributions of Study Variables and Features of Score Distributions, Change from Baseline/ Month 1 for FIM and AIM

The univariate distribution of item change scores (Month 3 minus Baseline/ Month 1, Month 8 minus Baseline/ Month 1, and Month 8 minus Month 3) will be tabulated for the FIM and AIM, both in terms of distributional characteristics of change and frequency of responses. Distributional characteristic tables will include the SD of the change distribution, median change, first and third quartiles, and 95% CIs. Change analyses will be limited to those PLWHIV completing questionnaires at Baseline/ Month 1 and each respective timepoint. Categorical data for the FIM and AIM will be presented in shift analyses showing the frequency of change by the degree of shift across response categories and will be presented for Baseline/ Month 1 to Month 3, Baseline/ Month 1 to Month 8, and Month 3 to Month 8.

4 Fidelity to Treatment in Dosing Window

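### The Missing count for the FIM and AIM mean score covers only respondents with exactly one item, so blank scales and unreturned forms are unscored but uncounted

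*SAP*

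**What the plan says.** Participant SAP section 3.1 sets the scoring rule: "if at least 50% of the items are completed the scale will be scored by taking the mean of the completed items". With four items that means two, three or four. The section adds that a form "will not be scored if only one item is completed", and that "No missing data will be imputed".

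The note under participant Table 3.1 then gives two definitions for one Missing column.

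- **Item rows:** Missing is "the number of participants who were eligible to complete a survey at the respective timepoint but did not complete respective item". The percentage divides that count by "the number of people who filled out any portion of a survey the respective timepoint".
- **Mean-score row:** "Missing for the mean score counts any instance where a respondent completed one FIM item, not reaching the minimum of 2 items".

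The Table 3.2 note does the same for the AIM: "Missing for the mean score counts any instance where a respondent completed one AIM item, not reaching the minimum of 2 items".

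The one-item sentence also appears in:

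- staff SAP Tables 3.1 and 3.2, and change Tables 5.1 and 5.2;
- provider and Expert Panel SAP: provider Tables 3.1 and 3.2, provider change Tables 5.1 and 5.2, and Expert Panel Table 10.1.

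It does not appear in participant change Tables 5.1 and 5.2, or in Expert Panel Tables 10.2, 12.1 and 12.2.

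**The concern.** The mean score is unavailable for anyone with zero or one item. The counting rule covers only the second group. A participant who returns a form with the FIM blank, or who is eligible and returns no form, has no score and yet is not missing in the mean-score row. The same participant is missing in all four item rows beneath it.

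The participant analysis population is anyone who completes part of any questionnaire at any point (section 3), so people without a Month 8 form stay in it. A programmer who follows the note as written will print a scale-level missing count that is too small and does not reconcile with the rest of the table.

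**Working it through.** The shells hold only placeholders, so there is no printed figure to reproduce. The check is a count from the definitions.

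**Notation, for one timepoint.** N = number eligible; F = eligible with no form returned; Z = form returned with no scale items answered; O = exactly one item answered.

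- Score available: N − F − Z − O (section 3.1 scoring rule).
- Score unavailable: U = F + Z + O.
- Mean-score Missing as the note defines it: M = O.
- Shortfall: U − M = F + Z.
- Each item row shows at least F + Z, because its definition starts from those eligible.

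**Numbers.** N = 120 is the maximum enrolment (participant SAP section 2). F, Z and O are assumptions; no document gives them. The note states no percentage rule for the mean-score row, so the printed percentage below borrows the item-row denominator, which is people who filled out part of the survey (N − F). With Z = 2 and O = 1:

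| No form (F) | Respondents | Scored | Printed Missing | Actually unscored | In neither count |
|---|---|---|---|---|---|
| 6 (5%) | 114 | 111 | 1 (0.9% of 114) | 9 (7.5% of 120) | 8 |
| 12 (10%) | 108 | 105 | 1 (0.9% of 108) | 15 (12.5%) | 14 |
| 24 (20%) | 96 | 93 | 1 (1.0% of 96) | 27 (22.5%) | 26 |
| 36 (30%) | 84 | 81 | 1 (1.2% of 84) | 39 (32.5%) | 38 |

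In the 20% row, 93 scored + 1 missing = 94, which leaves 26 of 120 in neither count.

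I also varied the item pattern over (Z, O) = (0, 0), (2, 1) and (3, 3), with F from 5% to 30%. The printed figure then runs from 0 to 3.6%, and the true figure from 5% to 35%.

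**Percentage denominator.** In participant Tables 3.1 and 3.2 the item-row percentage puts eligible non-completers over people who filled out part of the survey. The numerator is not a subset of the denominator. In the 20% row, the item that the one-item respondent answered has 26 missing: 26/96 = 27.1% as defined, against 26/120 = 21.7% of those eligible. Participant Tables 4.1 and 4.2 already divide by those eligible, as do staff Tables 3.1 and 3.2.

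**Provider tables.** Item-row Missing in provider Tables 3.1 and 3.2 is counted among people who completed part of a survey at any time, not among those eligible at the timepoint. A corrected mean-score note alone would again leave two bases in one column.

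**The case against.** The best defence is that the sentence speaks of a respondent, and section 3.1 of partly completed forms. The row could be meant to report returned forms that could not be scored, with non-return left to the item rows. That narrows the gap but does not close it. A returned form with all four items blank is still unscored and uncounted: with Z = 2 and O = 1 the row prints 1 where 3 returned forms have no score.

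Several limits stand in full. The size rests on assumed counts. The participant SAP does not define who is eligible at a timepoint, and protocol section 9.1 removes people who permanently discontinue treatment from the study, so the relevant non-return rate could be low. Missing surveys are queried with sites (participant SAP section 2.1.4). Nothing in the documents says that non-response is greatest at Month 8. Section 3.1 itself needs no correction, because its 50% rule already leaves zero-item forms unscored.

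Three stronger readings are tempting, and the documents do not support them.

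- *A reader might infer that non-response is hidden.* It is not. The item rows of the same table, Tables 4.1 and 4.2, the shift tables and Appendix Table A1 all report missing responses item by item.
- *A reader might infer that the primary result is affected.* It is not. The primary endpoint is the proportion scoring 4 or 5 on every FIM item at Month 8. Table 2.1 bases it on completers of all four items and prints their number.
- *A reader might infer that participant change scores carry the same error.* They do not. The notes to participant Tables 5.1 and 5.2 lack the one-item sentence.

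**Conclusion.** The rule is wrong as written. Wherever the one-item sentence governs a cross-sectional FIM or AIM table, the mean-score Missing cell omits everyone with no items answered and every eligible person with no form. It understates scale-level missingness by F + Z.

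This is a secondary reporting error confined to the missing cells of the mean-score row. No estimate, confidence interval or scoring decision changes. The identity U − M = F + Z follows from the definitions alone. The claim that the printed figure will be small also needs few people to answer exactly one of four items, which is plausible but not documented. The percentages above are illustrations and depend on a non-return rate that the documents do not give.

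**What to change.** **Cross-sectional tables that carry the sentence** (participant, staff and provider Tables 3.1 and 3.2; Expert Panel Table 10.1). Replace it with: *Mean-score Missing = number eligible for the survey at that timepoint with fewer than two items completed (0 or 1, unreturned forms included). Missing % = that number divided by the number eligible at that timepoint.* Both parts are needed. Widening the numerator while keeping the respondents-only denominator would give 27/96 = 28.1% in the 20% row instead of 27/120 = 22.5%.

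**Item rows.** In participant Tables 3.1 and 3.2, divide by the number eligible, as Tables 4.1 and 4.2 do. In provider Tables 3.1 and 3.2, move item-row Missing and its percentage to the same basis.

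**Staff and provider change Tables 5.1 and 5.2.** These are limited to people who completed surveys at the months compared, so unreturned forms do not belong there. Use: *Mean-score Missing = number who completed surveys at both timepoints but had fewer than two items completed at either one.*

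**Participant change Tables 5.1 and 5.2.** No change on this point.

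Splitting the count into no form, no items and one item is optional but would show where the loss arises. The cost is a set of footnote and programming edits across three SAPs, with no new data. Where forms are unreturned or scales are blank, the printed missing counts for the mean score will be higher.
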